13.1 Continuation of treatment

Patients who are CR, PR, or SD will continue treatment per protocol.

13.2 Progressive disease (PD)

Patients who develop PD while receiving therapy will go to the survival follow-up phase.

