4.2 Survival Follow-up

	Survival Follow-up				
	q. 3 months until PD	At PD	After PD q. 3 months	Death	New Primary
Survival Follow-up	X	X	X	X	At each occurrence

1. If a patient is still alive 5 years after registration, no further follow-up is required.

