7.4.2 Definitions of Dose Limiting Toxicities (DLT)

A DLT will be defined as any Grade 3 or higher treatment-related toxicity that occurs during the DLT observation phase (8 weeks post Y90-RE), including:

- Any event resulting in a delay of cycle 2 by \geq 14 calendar days
- Any Grade 4 immune related adverse event (irAE)
- Any Grade 3 immune related AE (irAE) that does not resolve to \leq Grade 1 or to baseline with immunosuppressive therapy within 3 weeks
- Any Grade 3 colitis
- Any Grade 3 noninfectious pneumonitis irrespective of duration
- Grade 4 neutrophil count decreased lasting longer than 5 calendar days
- Grade 4 platelet count decreased
- Grade 3 platelet count decreased with hemorrhage
- Any \geq Grade 2 pneumonitis that does not resolve to \leq Grade 1 within 7 days of the initiation of maximal supportive care
- Any other Grade 3 irAE (excluding colitis or pneumonitis), that does not downgrade to Grade 2 within 7 days after onset of the event despite optimal medical management including systemic corticosteroids or does not downgrade to \leq Grade 1 or baseline within 14 days
- Liver transaminase elevation $> 8 \times$ ULN
- Total bilirubin $> 5 \times$ ULN
- AST or ALT $> 5-8 \times$ ULN with concurrent increase in total bilirubin $> 2 \times$ ULN without evidence of cholestasis or alternative explanations, e.g., viral hepatitis, disease progression in the liver, etc. (Hyll's Law). Exception: If it is present at cycle 3 but resolves at cycle 4 it is not a DLT.
- Any \geq grade 3 non-hematologic toxicity, except:
 - Grade 3 nausea or vomiting that lasts < 48 hours and resolves to \leq Grade 1 either spontaneously or with conventional medical intervention
 - Grade 3 nausea, vomiting, and diarrhea lasting < 72 hours in the absence of maximal medical therapy
 - Grade 4 vomiting and diarrhea lasting < 72 hours in the absence of maximal medical therapy
 - Grade 3 hypertension in the absence of maximal medical therapy
 - Grade 3 metabolic abnormalities (e.g. hypokalemia, hypomagnesemia, hypocalcemia, hypophosphatemia) that recover to \leq Grade 1 within 48 hours
 - \geq Grade 3 electrolyte abnormality lasting < 72 hours, is not clinically complicated, and resolves spontaneously or responds to conventional medical intervention.
 - Grade 3 or 4 elevation in serum amylase and/or lipase that are not associated with clinical or radiographic evidence of pancreatitis.
 - Grade 3 rash < 5 calendar days

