10.2.2 Reporting window

The adverse event collection window is from the first treatment (durvalumab or TheraSphere) through 30 days after the final administration (durvalumab or TheraSphere). Medical records and study records will be reviewed for up to 2 years post-embolization for radiation-induced adverse events. These will be assessed by the IDE-sponsor or delegate and captured in the electronic data capture system.

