13.0 Treatment/Follow-up Decision at Evaluation of Patient

Reason Off Treatment (from the Off-Treatment Form)	Go to CFU, SFU, or end folder rollout
1 = Treatment (Intervention) Completed Per Protocol Criteria	CFU
2 = Patient Withdrawal/Refusal After Beginning Protocol Therapy (Intervention)	CFU/SFU/No follow-up
3 = Adverse Events/Side Effects/Complications	CFU
4 = Disease Progression, Relapse During Active Treatment (Intervention)	SFU
5 = Alternative Therapy	SFU/No follow-up
6 = Patient Off-Treatment (Intervention) For Other Complicating Disease	SFU
7 = Death On Study	No follow-up
8 = Other	SFU/SFU/No follow-up
10 = Disease Progression Before Active Treatment (Intervention)	No follow-up
24 = Patient Withdrawal/Refusal Prior To Beginning Protocol Therapy (Intervention)	No follow-up

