13.7 Non-CNS PD

Patients who develop non-CNS PD at any time should go to event monitoring. These patients should be treated with alternative chemotherapy if their clinical status is good enough to allow further therapy.

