13.8 Unevaluable patients

If a patient fails to complete the first cycle of treatment, prior to administration of Y-90, for reasons other than toxicity, the patient will be regarded as unevaluable and will be replaced.

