17.2 MTD Definition and Determination

For this protocol, the patient must return to clinic for evaluation at least every **14** days +/- 5 days. Patients will be treated and observed for a minimum of **8** weeks post-Y90-RE before new patients are treated. Doses will not be escalated in any individual patient.

MTD Definition: The MTD will be defined as the highest dose level for which at most 1 out of 6 patients experience a dose-limiting toxicity (DLT). A total of 6 patients treated at the MTD will be sufficient to identify common toxicities at the MTD. For instance, those toxicities with an incidence of at least 25% will be observed with a probability of at least 82% (1-(1-0.25)⁶).

Refer to Section **7.42** for definition of dose-limiting toxicity (DLT).

MTD Determination:

This study will utilize an accelerated titration design. The dose levels to which patients will be assigned in sequential cohorts are listed in the table below.

		Immunotherapy (Durvalumab) Administrations					
		Pre-Y90 doses		Post-Y90 doses		Number of Administration of Durvalumab	
Dose level	Week -2	Week 0	Y90-Radio-embolization	Week 2	Week 4	Week 6	
					X		1
-2					X		2
-1							2
1 (start)	X	X					3
2	X	X		X			4
3	X	X		X	X		5
4	X	X		X	X	X	

In the first phase, a single patient will be treated per dose level until the first DLT is recorded. Once the first DLT is recorded, two additional patients are treated at the same dose level and the trial reverts to a standard 3+3 design in the second phase. At which time, decisions on when and how to dose escalate are described below.

Number of patients with DLT at a given dose level	Decision Rule
0 out of 3	Enter 3 patients at the next higher dose level
1 out of 3	Enter up to 3 additional patients at the same dose level. 
 • If 0 of these 3 patients experience DLT, proceed to the next dose level. • If 1 or more of these 3 patients experience DLT, then dose

	escalation is stopped, and this dose is declared the maximally administered dose. Three (3) additional patients will be entered at the next lowest dose level if only 3 patients were treated previously at that dose.
≥2 out of 3	Dose escalation will be stopped. This dose level will be declared the maximally administered dose. Three (3) additional patients will be entered at the next lowest dose level if only 3 patients were treated previously at that dose.

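### Follow-up after progression inside the 8-week DLT window is contradictory, and no rule says whether a patient not observed to week 8 is DLT-evaluable

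*Combined protocol and SAP*

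**What the plan says.** The sections that bear on a patient who progresses after Y90-RE but before week 8 are these.

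- **13.2:** "Patients who develop PD while receiving therapy will go to the survival follow-up phase". In the 13.0 table, reason 4 ("Disease Progression, Relapse During Active Treatment (Intervention") is likewise routed to survival follow-up.
- **4.2:** the survival schedule has a single row, survival status. After progression its column reads "After PD q. 3 months". There is no examination, adverse event or laboratory row.
- **13.7:** "Patients who develop non-CNS PD at any time should go to event monitoring". Section 4 has no schedule under that name. The same section has these patients move to other chemotherapy if fit, and does not mention an open DLT window.
- **7.4.2:** a DLT is a qualifying toxicity that "occurs during the DLT observation phase (8 weeks post Y90-RE").
- **17.2:** patients are treated and observed for at least 8 "weeks post-Y90-RE before new patients are treated", with clinic visits at least every 14 days. No exception is made for progression.
- **10.2.2:** adverse events are collected from first treatment "through 30 days after the final administration (durvalumab or TheraSphere"). Record review for up to 2 years is for radiation-induced events only.
- **13.8:** "If a patient fails to complete the first cycle of treatment, prior to administration of Y-90, for reasons other than toxicity", the patient is unevaluable and is replaced. Nothing comparable covers a patient lost to observation after Y90-RE.
- **17.5.3:** its definition of an evaluable subject serves efficacy and sets no minimum follow-up.

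**The concern.** The escalation decisions in 17.2 count patients with a DLT, and that count presumes each patient was watched for 8 weeks. A patient who progresses at, say, week 3 and is handled under 13.2 leaves the visit schedule before the window closes. If no DLT has been recorded by then, the plan does not say whether the patient is DLT-evaluable, is replaced, or counts as having no DLT. Read literally, the decision table sees a patient without a DLT.

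The laboratory criteria are the most exposed. Section 7.4.2 defines DLTs by transaminases above 8 times ULN, bilirubin above 5 times ULN and Grade 4 platelet decrease, none of which is reliably seen unless blood is drawn. Its combined transaminase and bilirubin criterion also turns on whether an abnormality present at cycle 3 has resolved at cycle 4, which cannot be judged without the cycle 4 tests. Section 1.2.2 itself cites Grade 3 or 4 hyperbilirubinemia in 13% of a 531-patient glass-microsphere series, so late hepatic events are not remote. Safety is the primary goal, and in the first phase one patient decides each step.

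**Working it through.** **1. The plan's own figures.** Section 17.2 states at least 82% probability of seeing a toxicity of 25% incidence among 6 patients: 1 − (1 − 0.25)^6 = 0.822, which reproduces. The 9 evaluable patients in 17.3 match 1 + 1 + 1 + 6 (my reading: one each at levels 1–3, six at level 4). Both take every patient as fully observed.

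**2. Adverse event collection against the DLT window.** Day 0 is Y90-RE and the window closes on day 8 × 7 = 56. Collection under 10.2.2 ends on the nominal day of last administration + 30.

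| Last administration | Collection ends | Short of day 56 by |
|---|---|---|
| Week 0 (day 0) | day 30 | 26 days |
| Week 2 (day 14) | day 44 | 12 days |
| Week 4 (day 28) | day 58 | none |
| Week 6 (day 42) | day 72 | none |

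If progression ends dosing, a patient progressing at week 3 had the last administration at week 0 or week 2. At level 1 it is always at week 0. For patients who stay in the 4.1 schedule, the adverse event and laboratory rows up to the end-of-treatment visit (week 8, footnote 12) cover the remaining days. For a patient moved out of that schedule, only 10.2.2 remains, and it schedules no laboratory tests.

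**3. The routing compared.** 13.2 and reason 4 give survival follow-up, with no safety assessment. 13.7 gives event monitoring, with no schedule. Even if event monitoring means the clinical follow-up column of 4.1, which does carry adverse event and laboratory rows, those visits are required only every 3 months and do not replace the two-weekly visits to week 8. 17.2 requires the 8 weeks but gives no visits for a patient routed elsewhere.

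**4. What a truncated record does.** The documents give neither a true DLT rate p nor the fraction f of DLT risk observed before truncation. I assume p = 0.25, 0.33, 0.50 and f = 0.25 to 0.75; a truncated patient then shows a DLT with probability p·f.

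*Single-patient phase*, chance of no recorded DLT = 1 − p·f. *3+3 phase*, chance of escalating = P(0 of 3) + P(1 of 3) × P(0 of next 3), with one truncated patient in the first three.

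| p | Single, full | Single, truncated | 3+3, full | 3+3, one truncated |
|---|---|---|---|---|
| 0.25 | 0.750 | 0.812–0.938 | 0.600 | 0.630–0.690 |
| 0.33 | 0.670 | 0.752–0.917 | 0.434 | 0.471–0.545 |
| 0.50 | 0.500 | 0.625–0.875 | 0.172 | 0.207–0.277 |

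Example, p = 0.33 and full follow-up: 0.67^3 + 3 × 0.33 × 0.67^2 × 0.67^3 = 0.301 + 0.444 × 0.301 = 0.434.

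*Detection among six*, with m truncated: 1 − 0.75^(6−m) × (1 − 0.25f)^m. The 82.2% becomes 77.8%–80.7% for m = 1 and 72.2%–79.1% for m = 2.

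**The case against.** The strongest reply is that 13.2 names a destination and not a time. Other sections carry no exception for progression: 17.2 requires 8 weeks of observation, footnote 12 fixes the end-of-treatment visit at week 8, 10.2.2 and 10.5.3 keep collecting for 30 days, and 10.5.5 requires DLTs to be reported. A reader might infer that progressors are transferred immediately and that safety observation simply stops. The documents do not say that, and 13.7 routes most progressors elsewhere. This stands, but it shows a conflict between sections and not a resolution. The 30-day rule still falls short after a week-0 or week-2 dose, and 17.2 supplies no visits to a patient in survival follow-up.

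Second, progression inside the window should be limited. The first post-baseline scan is at week 8 (11.1, footnote 12), 11.1 requires mRECIST as well as iRECIST criteria, and iRECIST requires confirmation. Early progression would therefore be mainly clinical or found on unscheduled imaging. This also stands. However, 17.5.3 accepts clinical progression (with DSMC confirmation), and all patients have had 2 or 3 prior lines of therapy.

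Third, level 1 has no protocol treatment after week 0, so 13.2 and reason 4 may not reach it, and reason 1 with clinical follow-up may apply. That is a fair reading. But 13.7 applies at any time, and 13.5 and 13.6 lead to survival follow-up at progression after cycles end, so level 1 is also unsettled.

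**Conclusion.** The point holds as an unreconciled conflict plus a missing definition. Sections 13.0, 13.2, 13.7, 10.2.2 and 17.2 disagree on follow-up after progression within the DLT window, and no rule settles DLT evaluability after Y90-RE. The day-count shortfall of 26 or 12 days follows from the documents. The escalation and detection figures rest on my assumed p and f; they show direction and rough size, given that a truncated patient occurs.

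Three stronger readings are not supported. First, the plan does not state that such a patient counts as DLT-free; that is only the default from silence. Second, a truncated single patient can clear an escalation step but cannot alone set the MTD, which allows at most 1 DLT in 6 patients. Third, the frequency is unknown. A reader might assume that a fraction r of patients progress early and compute 1 − (1 − r)^3 over levels 1–3, giving 14%, 27% or 49% for r = 5%, 10% or 20%. No document supports any r, level 1 may not belong in the count, and the result is the chance of a truncated record, not of a missed DLT.

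**What to change.** 1. Reconcile 13.0 (reason 4), 13.2, 13.7 and 10.2.2 with 17.2. The adverse event and laboratory assessments already in 4.1 should continue to week 8 after Y90-RE whatever the progression status, with survival follow-up starting afterwards. Check 13.5 and 13.6 for the same conflict, and either give event monitoring a schedule in Section 4 or drop the term.
2. Extend the 10.2.2 window so that it never closes before the DLT window does.
3. Define DLT evaluability in 17.2. A patient with a DLT is evaluable at any time. A patient without a DLT who is not observed to week 8 is not DLT-evaluable, does not count as DLT-free in the decision table, and is replaced. Align 13.8 with this.
4. State how the DLT record is read if another anticancer treatment starts before week 8, since 13.7 foresees that.

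None of this changes a dose or a treatment rule. The cost is wording, visits that are already scheduled, occasionally one more patient at a level, and a slightly longer escalation: each replacement at level 1 or above needs about 10 weeks from first dose to end of window (week −2 to week 8).

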13.3 Off protocol treatment

Patients who go off protocol treatment for reasons other than PD will go to the event-monitoring phase per Section 4.0.

13.4 Observation

If the patient has achieved CR, PR, or SD, the patient will be observed at 3 months, every 3 months for 1 year, and then every 3 months for up to 5 years from time of registration.

13.5 Duration of therapy for CR

Patients who achieve a CR will receive a maximum total of cycles for assigned cohort. After completion of cycles, they should be observed (see 13.4 above) every 3 months for 2 years or until PD and then they will go to survival follow-up.

13.6 Duration of therapy for PR or SD

Patients who are in PR or SD will continue on therapy for a maximum total of cycles for assigned cohort. After completion of cycles, they should be observed (see 13.4 above) every 3 months for 2

years or until PD and then they will go to survival follow-up (see 13.5 above). Subsequent treatment is at the discretion of their attending physician

13.7 Non-CNS PD

Patients who develop non-CNS PD at any time should go to event monitoring. These patients should be treated with alternative chemotherapy if their clinical status is good enough to allow further therapy.

13.8 Unevaluable patients

If a patient fails to complete the first cycle of treatment, prior to administration of Y-90, for reasons other than toxicity, the patient will be regarded as unevaluable and will be replaced.

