The trial will be performed in **18 subjects** with mCRC with liver metastasis and the safety of immunotherapy (durvalumab) with Y90-RE will be investigated in an accelerated titration design. This would allow a maximum tolerated dose with the minimum number of subjects. At any point as noted below if there is a DLT, the study design defaults to a standard 3+3 design. Assuming a 10% loss of subjects after enrollment, the dose escalation design will require at least 9 evaluable subjects to establish the highest dose level as the maximum tolerated dose (MTD). If less than 18 subjects are administrated in the dose escalation, the rest of subjects will be administrated the MTD in the expansion cohort. **Sample size of maximum of 18 was based on an accelerated titration design and on the correlative studies including pre- and post-biopsies. The primary goal of this study is to establish safety and with a secondary goal of looking at biomarkers and other immune signals as noted.**

This study will utilize an accelerated titration design. The dose levels to which patients will be assigned in sequential cohorts are listed in the table 1.

Table 1. Dose escalation cohort of durvalumab*

		Immunotherapy (Durvalumab) Administrations						Number of Administration of Durvalumab	
Dose level	Pre-Y90 doses		Post-Y90 doses			Week2	Week4	Week6	
	Week-2	Week0	Week2	Week4	Week6				
-2					X				1
-1				X	X				2
1 (start)**	X	X							2
2	X	X		X					3
3	X	X		X	X				4
4	X	X	X	X	X				5

* Please note: As noted above, the rationale for the proposed dosing schema is keeping in mind the timing of toxicities that are typically seen post Y90-RE. Most patients have elevation of their liver enzymes the first 1-2 weeks. Therefore, with the dosing escalation, we did not include the added dose at week 2 for the first dose escalation (dose level 2). Patients get fixed dosing of immunotherapy, which is the case for all immunotherapy-based studies. Depending on the dose level, patients can get a maximum of 2 doses before and 3 doses post Y90-RE (dose level 4).

**While dose level 1 and dose level -1 have the same number of durvalumab administrations, they are different since dose level 1 get 2 doses pre-Y90-RE ('priming doses of immunotherapy before Y90-RE) while dose level -1 only get 2 doses post-Y90-RE.

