A single patient will be treated per dose level until the first DLT is recorded. Once the first DLT is recorded, two additional patients are treated at the same dose level and the trial reverts to a standard 3+3 design. At which time, decisions on when and how to dose escalate are described below.

Number of patients with DLT at a given dose level	Decision Rule
0 out of 3	Enter 3 patients at the next higher dose level
1 out of 3	Enter up to 3 additional patients at the same dose level. 
 • If 0 of these 3 patients experience DLT, proceed to the next dose level. • If 1 or more of these 3 patients experience DLT, then dose escalation is stopped, and this dose is declared the maximally administered dose. Three (3) additional patients will be entered at the next lowest dose level if only 3 patients were treated previously at that dose.
≥ 2 out of 3	Dose escalation will be stopped. This dose level will be declared the maximally administered dose. Three (3) additional patients will be entered at the next lowest dose level if only 3 patients were treated previously at that dose.

Up to 6 patients will be treated at each dose level. The MTD will be defined as the highest dose level for which at most 1 out of 6 patients experience a DLT. If DLT meets the stopping boundaries set by the above dose algorithm at dose level 1 (for example, more than 1 out of 3 or more than 1 out of 6 patients), the next cohort of 3 patients will be entered at the dose level of -1. If dose level -1 meets the stopping boundaries, the next cohort of 3 patients will be entered at dose level -2.

If an MTD is determined, an expansion cohort using the RP2D will be carried out in additional patients for a maximum of 18 patients. If an MTD is not determined, the expansion cohort will utilize the dosing scheme from cohort 4.

After the end of treatment visit (EoT) subjects (if applicable) are to resume the previously discontinued chemotherapy until all cycles have been administered or treatment is discontinued as per regular standard of care or secondary resection if deemed a candidate. The decision to resume the previously discontinued chemotherapy is to be done at investigators discretion. As the patients will commence a different treatment regime, no active follow-up will be done as part of this study other than progression free survival and overall survival.

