7. Gross (dipstick) urine examination: Leukocytes, nitrite, pH, protein, glucose, ketone, urobilinogen, bilirubin, blood (hemoglobin and erythrocytes). If abnormalities are detected by dipstick, then a microscopic sediment test should also be performed. If a UTI is suspected, it can be treated.
8. Durvalumab administration over 60 minutes. Following infusion, subjects must be observed for 30 minutes post infusion for potential infusion related reactions. The number of doses administered is per dose level for each patient cohort.
9. The 2nd durvalumab dose can be done \leq 5 days prior to Y90-RE or same day as long as it is before the Y90-RE.
10. Blood biomarkers will be collected in the morning of visit. Kits are required.
11. Tissue specimens must be collected the following timepoints: pre-treatment [screening/prior to cycle 1 of Durvalumab (fresh as well as archived if available)], and post-treatment. Kits are required (banking, clinical as well as real-time send out).
12. Visit will occur 8 weeks after Y90-RE.
13. Clinical follow-up visits will be performed at least every 3 months (or as per standard physician practice) for 2 years.
14. Cohort 1- Durvalumab given at cycle 1 and cycle 2 only
15. Cohort 2- Durvalumab given at cycle 1, 2, and 4
16. Dose escalation cohort- Durvalumab given cycle 1, 2, 4 and 5
17. Dose expansion cohort- Durvalumab given cycle 1, 2, 3, 4, and 5
18. As long as the lesion is amenable to a biopsy and is done, the biopsy can be done on the Tc-99m labelled MAA eligibility mapping day to save patient a visit. Has to be prior to anti-PD1 therapy though. From a safety perspective since we need to know about the shunting to other organs prior to the Y90-RE, the mapping can be done during the screening or even prior to considerations for this study if already performed within 12 months of intended Y90-RE, it would not need to be repeated unless as per interventional radiology. Biopsy still needs to be done as noted.
19. If there is complete response of the lesion in the field of Y90-RE, tissue biopsy of the field would still be done to assess for the immune changes and an alternative tumor lesion can be biopsied for testing of the tumor itself.
20. At the time of progression, patient would be approached for a tissue biopsy and research blood sampling similar to the end of treatment visit.

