13.10 Major violation

A patient is deemed a *major violation*, if protocol requirements regarding treatment in cycle 1 of the initial therapy are severely violated that evaluability for primary end point is questionable. If the patient received treatment, the patient may continue treatment at the discretion of the physician as long as there are not safety concerns. The patient will continue in the Active Monitoring/Treatment phase of the study, as per section 4.0 of the protocol.

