17.5.3 Overall Response Rate

Overall response rate is defined as the proportion of evaluable patients that have achieved a complete response or partial response using mRECIST evaluation criteria. ORR will be evaluated at 2 months post-Y90RE treatment (\pm 5 business days).

ORR will be analyzed descriptively as a point estimate with a 95% confidence interval.

Results will be reported consistent with RECIST v1.1 (Appendix A.9).

An “evaluable subject” for the purpose of evaluation of the combinatorial therapy is one who receives both Y90-radioembolization and at least 1 dose of durvalumab.

Subjects who do not receive Y90-RE or received only a single incomplete dose of immunotherapy (i.e., allergic reaction), are considered non-evaluable for assessment of efficacy. These subjects would be replaced for the proposed sample size of 18.

All subjects included in the study must be assessed for response to treatment, even if there are major protocol treatment deviations or if they are ineligible.

Each subject will be assigned one of the following categories: 1) complete response (mRECIST), 2) partial response (mRECIST), 3) stable disease (mRECIST), 4) progressive disease (mRECIST), 5) early death from malignant disease, 6) early death from toxicity, 7) early death because of other cause, or 9) unknown (not assessable, insufficient data).

Category 4 (protocol specific definition): includes clinical progression as determined by the principal investigator and confirmed by the independent data and safety monitoring committee (DSMC).

Category 5 (protocol specific definition): death from malignant disease as determined by the principal investigator and confirmed by the independent data and safety monitoring committee (DSMC).

Category 6 (protocol specific definition): death from toxicity as determined by the principal investigator and confirmed by the independent data and safety monitoring committee (DSMC).

Category 7 (protocol specific definition): includes death not meeting categories 5 or 6, or death defined as not otherwise specified.

Category 9 (protocol specific definition): includes subjects who did not receive radioembolization, or who did not receive at least 1 complete infusion of durvalumab, or who did not undergo follow-up imaging (other than for clinical progression, toxicity, or death), or subjects who are lost to follow-up.

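### DLT evaluability never depends on the post-Y90 durvalumab doses that separate levels 2–4 from level 1, so one under-dosed patient can clear level 2 or level 3

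*Combined protocol and SAP*

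**What the plan says.** **What separates the levels.** In Table 1 (section 1.4.6), levels 1–4 share the two pre-Y90 doses. Levels 2, 3 and 4 add one, two and three doses after Y90-RE. The test schedule agrees for level 2: "Cohort 2- Durvalumab given at cycle 1, 2, and 4", where cycle 4 is week 4.

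**How a level is cleared.** "A single patient will be treated per dose level until the first DLT is recorded" (1.4.6, repeated in 17.2). After the first DLT a 3+3 design applies, and the MTD needs at most 1 DLT in 6 patients.

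**Who counts.** Four places bear on this:

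- 13.8 replaces a patient on this condition only: "If a patient fails to complete the first cycle of treatment, prior to administration of Y-90, for reasons other than toxicity".
- 13.10, on major violations, uses this test: "if protocol requirements regarding treatment in cycle 1 of the initial therapy are severely violated that evaluability for primary end point is questionable". It states no replacement.
- 17.2 requires patients to be treated and observed for at least 8 "weeks post-Y90-RE before new patients are treated". That sets a time, not a number of doses.
- 17.5.3, in the response section, says that an evaluable subject "is one who receives both Y90-radioembolization and at least 1 dose of durvalumab".

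Sections 1.4.6 and 17.3 say that 9 evaluable patients are needed, without defining evaluable for DLT purposes.

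**The concern.** DLT counts drive every escalation decision and serve the primary safety goal. A DLT-free outcome supports a level only if the patient was exposed to what makes that level different. Here the difference lies entirely after Y90-RE, while the only replacement rule for dose decisions looks at cycle 1, before Y90-RE. Applied as written, 13.8 leaves a patient who stops after cycle 2 in the count at the assigned level. With one patient per level, the trial can then move past a regimen that nobody has received. If missing doses lowers the risk of a DLT, the error favours escalation.

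A related wording problem affects the same counts. The lead-in to 7.4.2 confines DLTs to the 8 weeks after Y90-RE, yet the list includes a delay of cycle 2. At levels 1–4 cycle 2 is given with Y90-RE (7.1.2), so such a delay arises before the window opens.

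**Working it through.** **1. The plan's own figures.** With no DLTs, the design needs 1 + 1 + 1 + 6 = 9 patients for levels 1–4, as 17.3 states. Section 17.2 says of 6 patients that "those toxicities with an incidence of at least 25% will be observed with a probability of at least 82" per cent; 1 − 0.75^6 = 0.822. Both reproduce.

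**2. Doses received if treatment stops after cycle 2** (Table 1). Level 2: 2 of 3. Level 3: 2 of 4. Level 4: 2 of 5. In each case this is the level 1 regimen. None of 13.8, 13.10, 17.2 or 17.5.3 removes such a patient from the DLT count.

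**3. Can this happen without a DLT?**

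- *Main route: an unresolved Grade 2 event.* Table 8.21 stops all protocol treatment if, for example, Grade 2 diarrhea/colitis or Grade 2 ALT, AST or bilirubin elevation has not resolved in 2 weeks. The DLT list in 7.4.2 names Grade 2 only for pneumonitis, and its only delay item concerns cycle 2. At level 2, onset by week 2 without resolution means stopping before the week 4 dose, the only dose that distinguishes the level. Section 1.4.6 expects liver enzyme elevation in most patients in the first 1–2 weeks, without giving grades. After the first two cycles, section 8.0 makes Table 8.21 a guideline.
- *Narrower route: a first Grade 3 infusion reaction that resolves within 6 hours.* It is exempt as a DLT in 7.4.2, but Table 8.21 and Appendix VII both call for permanent discontinuation. At level 3, such a reaction at week 4 removes the week 6 dose.
- *Marginal route: progression.* Section 13.2 moves the patient to survival follow-up, but the first planned scan is at the end-of-treatment visit, 8 weeks after Y90-RE and after every planned dose.

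**4. How often?** Let u be the chance that a patient misses level-defining doses without a DLT. The documents do not give u. Their only loss figure, 10% after enrollment, is not specific to missed doses. The values below are assumed.

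| u | At least one lone patient at levels 2 and 3 under-dosed, 1 − (1 − u)^2 | At least one of 6 at level 4 under-dosed, 1 − (1 − u)^6 |
|---|---|---|
| 5% | 10% | 26% |
| 10% | 19% | 47% |
| 20% | 36% | 74% |
| 30% | 51% | 88% |

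**5. Effect on a one-patient decision.** Let pF and pP be the DLT risks with full and partial dosing, also assumed. The chance of clearing is (1 − u)(1 − pF) + u(1 − pP). With u = 0.20, pF = 0.40 and pP = 0.10, this is 0.48 + 0.18 = 0.66, against 0.60 if only fully dosed patients could clear. The share of clearances with no fully dosed patient is 0.18/0.66 = 27%. Over pF 0.30–0.50, pP 0.10–0.20 and u 0.10–0.30, that share runs from 11% to 44%.

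**6. Limiting case for the 6-patient statement.** If a 25% toxicity can occur only with the missed doses, detection is 1 − 0.75^5 = 76% with 5 of 6 fully dosed and 1 − 0.75^4 = 68% with 4.

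**The case against.** The strongest reply is that the documents are silent rather than wrong. Section 17.2 says treated as well as observed for 8 weeks, which could be read as treatment through week 6, and the 9-patient statements say evaluable. The detailed data and safety monitoring plan is held elsewhere (10.0) and cannot be checked. This shows that the status of an under-dosed patient is poorly defined, but it supplies no dose minimum and no replacement rule. The one rule that is stated, 13.8, does not catch these patients.

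Several stronger readings are tempting and should be resisted:

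- *Any of levels 2–4 can be established on one patient.* Level 4 has no level above it, and declaring it the MTD takes 6 patients. After the first DLT, cohorts of 3 apply.
- *The trial's ability to see a common toxicity falls to 68%.* That figure concerns 6 patients and gives no weight to partial exposure. On the no-DLT path 6 + 9 = 15 of 18 patients are at level 4, where detection is 1 − 0.75^15 = 98.7%, and still 1 − 0.75^10 = 94.4% if 5 were under-dosed. Expansion data, however, come after the escalation decisions.
- *Most early stops escape the DLT definition.* Grade 3 or higher related non-hematologic toxicity that stops dosing is mostly a DLT already.
- *Every under-dosed patient should be replaced.* Replacing those who stopped for non-DLT toxicity until tolerant patients complete the level would select for tolerance, could itself push the MTD upward, and departs from the limit in 13.8 to non-toxicity reasons.

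On 7.4.2, the cycle 2 delay is expressly listed, so it is evidently meant to count. What remains unclear is the status of other related toxicity before Y90-RE.

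**Conclusion.** The gap is real and should be fixed. It follows from the text alone: before the first DLT, level 2 or level 3 can be cleared by one DLT-free patient who did not receive that level's post-Y90 doses. In 3+3 cohorts and in the 6-patient MTD count it dilutes the evidence. It rests mainly on the Grade 2 route, with the qualification that Table 8.21 is guidance after cycle 2.

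The size is uncertain. The 19–51% range holds only for assumed under-dosing of 10–30%. An upward shift in the MTD also requires that missed doses lower DLT risk, which the documents neither state nor refute. The 7.4.2 conflict is a matter of reconciliation, and no size is claimed for it.

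**What to change.** 1. In 13.8, reconciled with 13.10, 17.2 and 17.5.3, define DLT-evaluable for dose decisions as either having had a DLT, or having received the durvalumab doses that define the assigned level and completed the 8-week window.
   - Replace patients who missed those doses for reasons other than toxicity.
   - Keep patients who missed them because of non-DLT toxicity in the level's count, and report their number and reasons at each escalation decision. Do not clear a level on such patients alone; add a patient at that level.
   - Keep everyone in the safety tables.
2. Reconcile the 7.4.2 lead-in (and 1.4.5–1.4.7 and 17.2) with the cycle 2 delay item. Treatment-related toxicity between first durvalumab and Y90-RE needs a stated DLT status. State also whether the Grade 3 or higher, treatment-related condition applies to that item.

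**Cost.** No new assessments. If every under-dosed patient led to one more enrolment, the no-DLT path would need 9/0.9 = 10.0, 9/0.8 = 11.3 or 9/0.7 = 12.9 escalation patients at u = 10%, 20% or 30%. Exempting the single level 1 patient gives 1 + 8/(1 − u) = 9.9, 11.0 or 12.4. If the protocol's 10% loss is additional, dividing these last figures by 0.9 gives 11.0, 12.2 or 13.8. All stay within 18. With 10–13 in escalation, 8 to 5 places remain for expansion instead of 9. Each added patient takes about 10 weeks (2 before and 8 after Y90-RE). One to four added strictly in sequence would mean 10 to 40 weeks, which matters against the 18-month accrual expectation in 17.4.
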